coincide with standard of care clinic visits. A portion of the immune monitoring blood sample will be used for RCR PCR per the FDA prior to EGFRvIII CAR infusion, and at 3, 6 and 12 months during standard of care clinic visits. Lastly, blood for evaluation of CRS (1 red, 1 purple top – 3mLs each) will be drawn prior to cell infusion, 1 and 4 hours after infusion, and on days 1, 2, 5, 10, and at approximately 28 days. Measurements for CRS include IL-2, IL-6, TNF α , IFN γ , GM-CSF, and C-reactive protein (CRP).

Patients will return to clinic approximately 28 days following the EGFRvIII CAR T cell infusion to be evaluated for cycles of standard of care 5-day TMZ at 150-200 mg/m²/day for the first 5-day cycle, followed by 200 mg/m²/day (if tolerated by the patient) for 5-days every 28 days at the discretion of the treating oncologist. This will result in an approximately > 30-day delay between the last TMZ administration prior to EGFRvIII CAR T cell infusion and the TMZ cycle initiated after the study drug infusion. This delay in the TMZ cycle after the CAR T cell infusion is done in an attempt to decrease the chance of study drug washout by TMZ.

Tumor progression will be documented histologically, unless there are clinical contraindications, to exclude inflammatory responses presenting as radiographic or clinical changes, which could indicate a potentially toxic or therapeutic responses and not tumor progression. If tissue is obtained through the Duke Brain Tumor Center Biorepository IRB# Pro00007434, it will be used to confirm tumor progression histologically, and to assess immunologic cell infiltration and EGFRvIII antigen escape at the tumor site. Patients will be eligible for additional adjuvant therapy at the time of tumor progression.

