9.1.2 Definition of Dose-Limiting Toxicity (DLT)

The DLT observation period is the 4 weeks after EGFRvIII CAR T cell infusion. Toxicities will be graded according to the NCI CTCAE version 4 criteria. A DLT will be defined as any Grade IV event of any duration that is at least (possibly, probably, or definitely) attributable to EGFRvIII CARs, or any Grade III toxicity that is at least (possibly, probably, or definitely) attributable to EGFRvIII CARs that is not reversible within 4 weeks. DLT definition includes and will be reported to FDA all of the following:

- a. Any treatment-emergent CTCAE Grade 4 or 5 CRS.
- b. Any treatment-emergent CTCAE Grade 3 CRS that do not resolve to \leq Grade 2 within 7 days.
- c. Any treatment-emergent autoimmune toxicity \geq Grade 3.
- d. CTCAE grade 3-5 allergic reactions related to the study cell infusion.
- e. CTCAE grades 3 and greater organ toxicity (cardiac, dermatologic, gastrointestinal, hepatic, pulmonary, renal/genitourinary, or neurologic) not pre-existing or due to the underlying malignancy and occurring within 30 days of study product infusion.

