9.4 Definition of Evaluable Subjects, On Study, and End of Study

While all patients who received any EGFRvIII CAR T cells will be included in safety summaries for the purposes of monitoring and reporting of adverse events to appropriate agencies, patients evaluable for determination of the MTD will include:

- Patients who receive the entire CARs infusion (i.e. the infusion is not stopped prematurely), and 2) have 4 weeks of follow-up for adverse events after the infusion
- Patients who receive the entire CARS infusion (i.e. the infusion is not stopped prematurely) and terminated follow-up prematurely during the 4 week follow-up period after having experienced a DLT.
- Patients who terminate infusion before completion due to a DLT

For the efficacy analyses, evaluable patients will include two groups of patients: all patients, and the subgroup of patients who receive EGFRvIII CAR. Once a patient's eligibility is confirmed after completion of XRT/TMZ, that subject will be considered "on study". The rationale for taking a patient off study will be documented. Please see Section 12.7 for information on patient withdrawals.

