The patient will be scheduled for CAR T cell (or CAR T cell labeled with ¹¹¹In) infusion at least 48 hours (+72 hours) after their last dose of DI TMZ. In the expanded cohort group, 3 days of whole body planar imaging and SPECT/CT imaging will be done following infusion on days 1, 2, and 3. Note, if there is no signal on whole body planar imaging, the radiologist may decide not to perform SPECT/CT. Blood for immune monitoring will be taken on all patients at leukapheresis, pre-infusion, 1, 5, 10, and 28 days following infusion, and at 3 and 6 months post-infusion, and then yearly (until progression, death, or lost to contact). The return visits for immune monitoring at the 3, 6, and yearly will coincide with standard of care clinic visits. Blood for RCR PCR will be taken prior to cell infusion and at 3 and 6 months, and at one year as required by the FDA during routine clinic visits. Lastly, blood for evaluation of CRS will be drawn prior to cell infusion, 1 and 4 hours after infusion, and on days 1, 2, 5, 10, and at 28 days. Measurements for CRS include IL-2, IL-6, TNF α , IFN γ , GM-CSF, and CRP.

Blood samples will be archived annually thereafter if all previous testing has been negative.

Patients will return to clinic, as per standard of care, approximately 28 days after EGFRvIII CAR T cell infusion to be evaluated radiographically and clinically for cycles of standard of care 5-day TMZ at 150-200 mg/m²/day per the treating oncologist. This will result in a 28-day pause between the last cycle of TMZ

administered prior to EGFRvIII CARs and the first cycle administered after study drug infusion in order to decrease the chance of study drug washout from TMZ.

Table 6. Screening and On-Study Tests and Procedures

	Pre-XRT/TMZ Screening	Leukapheresis	Post-XRT/TMZ screening	DI TMZ Cycle 1	Post DI TMZ Cycle 1	DI TMZ Cycle 2 ¹	DI TMZ Cycle 3 ¹	Pre-CAR T Cell Infusion	CAR T Cell Infusion ²	5-day TMZ Cycles 4-12	Progression
Main study consent	X										
History and Physical	X		X		X ³			X ⁴		X ⁵	
Neurological Exam	X		X		X ³			X ⁴		X ⁵	
KPS	X		X		X ³			X ⁴		X ⁵	
Curran			X								
CBC w/ differential	X	X	X	X ⁶	X ³	X ^{6,3}	X ⁶	X ⁴		X ⁷	
CMP	X	X	X		X ³	X ³		X ⁴		X ⁸	
Beta HCG	X	X									
CRS									X ⁹	X ¹⁰	
Immune Monitoring		X ¹¹							X ¹²	X ¹³	X ¹³
CAR T Cells									X ¹⁴		
DI Temodar				X ¹⁵		X ¹⁵	X ¹⁵				
5-day Temodar										X ¹⁶	
Vitals	X		X		X ³			X ³	X ¹⁷	X ⁵	
MRI	X		X		X ³			X ³		X ⁵	
Pathology testing	X										X

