Adverse Events									Ongoing		
Con Meds									Ongoing		

¹ Some patients may not receive DI TMZ cycle 3 or cycles 2 and 3, please see Section 9.1 for details about DI TMZ requirements.

² 48 hours (+72 hours) after last dose of DI TMZ

³ ± 7 days from the last dose of TMZ

⁴ Within 2 days prior to CAR T Cell infusion.

⁵ Prior to Cycle 4 and then prior to every other Cycle (Cycle 6, 8, etc), at the discretion of the treating physician.

⁶ Day 14 (± 3 Days) of the TMZ cycle.

⁷ Day 21 (± 3 days) and day 28 (± 7 days) of each 5-day TMZ cycle

⁸ Day 28 (± 7 days) of each 5-day TMZ cycle

⁹ Prior to CAR T Cell Infusion, and at 1 and 4 hours and days 1, 2, 5, and 10 post CAR T Cell infusion. Draw 1 red top and 1 purple top (3 mL each) and 1 gold top at each time point.

¹⁰ 28 days post CAR T Cell Infusion. Draw 1 red top and 1 purple top (3mL each) and 1 gold top.

¹¹ 2 red tops (10 mL each).

¹² Prior to CAR T Cell Infusion on day 22 (+3 day window), and at 1, 5, and 10 days after the infusion (9 yellow tops (8.5mL each) and 1 red top (10mL) at each time point.

¹³ 1, 3, 6, and 12 months post CAR T Cell infusion and then yearly and at progression. Draw 9 yellow tops (8.5mL each) and 1 red top (10mL) at each time point. Draws will coincide with standard of care return clinic visits.

¹⁴ At least 48 hours after last dose of DI TMZ. Patients will be pre-medicated 30-60 minutes prior to infusion with acetaminophen (650 mg po) and Benadryl (25 mg by mouth) to reduce infusion-related reactions. Patients must be on stable of decreasing steroid dose (≤ 4 mg/day) 2 weeks prior to CAR T cell infusion.

¹⁵ Days 1-21 of a 28-day cycle, at the discretion of the treating physician.

¹⁶ 5 day TMZ to be taken on days 1-5 of a 28 day cycle. The first cycle of 5-day TMZ will be initiated approximately 1 month after CAR T Cell infusion.

¹⁷ Vital signs will be measured prior to the CAR T cell infusion and every 15 minutes for 1 hour post-infusion. Measurements to be reported include temperature in Celsius or Fahrenheit, pulse (beats per minute), respiratory rate (breaths per minute) and blood pressure.

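### Table 6 schedules no CBC or CMP in the 4 weeks after infusion, so an isolated, asymptomatic laboratory DLT can be counted as no DLT

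*Combined protocol and SAP*

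**What the plan says.** **Laboratory schedule (Section 12, Table 6).** CBC with differential and CMP are marked at the pre-infusion visit, within 2 days before infusion (footnote 4). Both rows are empty in the infusion column. The next entries belong to the 5-day TMZ cycles:

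- CBC on "Day 21 (± 3 days) and day 28 (± 7 days) of each 5-day TMZ cycle" (footnote 7); CMP at the second of those times only (footnote 8).
- Footnote 16 dates these cycles: "The first cycle of 5-day TMZ will be initiated approximately 1 month after CAR T Cell infusion".
- The visit in footnote 5, "Prior to Cycle 4 and then prior to every other Cycle (Cycle 6, 8, etc), at the discretion of the treating physician", is attached to history and physical, neurological examination, KPS, vital signs and MRI. It is not attached to CBC or CMP.

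Section 12 says that patients return at about day 28 "to be evaluated radiographically and clinically for cycles of standard of care 5-day TMZ". It names no laboratory test for that visit.

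**DLT definition (Section 9.1.2).** The observation period is 4 weeks. The general rule reads "A DLT will be defined as any Grade IV event of any duration", provided that the event is at least possibly attributable to the cells. Item e adds the following, if it occurs within 30 days and is neither pre-existing nor due to the malignancy:

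- "CTCAE grades 3 and greater organ toxicity (cardiac, dermatologic, gastrointestinal, hepatic, pulmonary, renal/genitourinary, or neurologic"

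**Evaluability and detection.** Section 9.4 counts a patient towards the MTD who receives the whole infusion and who "have 4 weeks of follow-up for adverse events after the infusion". It asks for no laboratory result. Section 13 finds adverse events by asking the patient or by evaluating study assessments. Section 13.1 expects laboratory events to be recorded from grade 1.

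**The concern.** Part of the DLT definition can only be seen in a blood test. A Grade 3 rise in liver enzymes or creatinine may cause no symptoms. The rule on Grade III toxicity that does not reverse within 4 weeks needs repeat values when the toxicity is a laboratory one. Section 9.1.3 names tumor lysis syndrome as a risk, with potassium and phosphate release and possible kidney failure, yet no chemistry is scheduled while DLTs are being counted. By contrast, the DI TMZ cycles before infusion do have a CBC at day 14 (footnote 6).

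Table 4 escalates on the 4-week DLT count, and Section 15.7 uses the patients treated at the MTD to estimate the DLT rate. A laboratory DLT that nobody measured enters both as a patient without DLT. Taken alone, that error lowers the observed rate and favours escalation.

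**Working it through.** **1. When do the first scheduled tests fall?** The plan states no post-infusion day for them, so there is no figure to reproduce. Take infusion as day 0 and let the first 5-day cycle start on day S. Cycle day d then falls on day S + d − 1. The first CBC is cycle day 21 (18 to 24) and the first CMP is cycle day 28 (21 to 35).

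The text gives S in three ways:

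- Footnote 16: about 1 month, so about day 28 to 31.
- Section 9.1: "This will result in an approximately > 30-day delay between the last TMZ administration prior to EGFRvIII CAR T cell infusion" and the next cycle. The last TMZ dose is 2 to 5 days before infusion (48 hours, plus up to 72), so 30 − 5 = day 25 at the earliest.
- Section 12: a 28-day pause, so 28 − 5 = day 23 to 28 − 2 = day 26.

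Sections 9.1 and 12 describe the pause differently and need reconciling. The result below holds under either.

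| Start S | First CBC (window) | First CMP (window) |
|---|---|---|
| 23 | 43 (40–46) | 50 (43–57) |
| 25 | 45 (42–48) | 52 (45–59) |
| 28 | 48 (45–51) | 55 (48–62) |
| 31 | 51 (48–54) | 58 (51–65) |

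The earliest possible values are day 40 for CBC and day 43 for CMP, both after the more generous 30-day limit. A CBC by day 30 would need S ≤ 30 − 17 = 13, and a CMP S ≤ 30 − 20 = 10. If 5-day TMZ is not started, no later CBC or CMP is scheduled at all.

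**2. Does another entry fill the gap?** Footnote 3 allows ± 7 days from the last TMZ dose. With infusion 2 to 5 days after that dose, its outer edge could reach post-infusion day 2 to 5. It belongs to columns that precede the pre-infusion visit, however, so it is not a post-infusion test. Sections 9.1, 12.2, 12.5 and 12.8 add no CBC or CMP after infusion.

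**3. What could it do to escalation?** Under Table 4, a dose is passed with 0 of 3 DLTs, or with 1 of 3 followed by 0 of 3. If the true DLT rate is p and a share u goes unseen, the observed rate is q = p(1 − u), and

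P(escalate) = (1 − q)³ + 3q(1 − q)⁵.

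The documents give no value for u; 5% is assumed. For p = 0.30, all seen: 0.70³ + 0.90 × 0.70⁵ = 0.343 + 0.151 = 0.494. With q = 0.285: 0.715³ + 0.855 × 0.715⁵ = 0.525.

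| True rate | All seen | 5% unseen | Rise (points) |
|---|---|---|---|
| 0.10 | 0.906 | 0.914 | about 1 |
| 0.20 | 0.709 | 0.730 | about 2 |
| 0.25 | 0.600 | 0.627 | about 3 |
| 0.30 | 0.494 | 0.525 | about 3 |

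For the 18 patients planned at the MTD and a true rate of 0.20, expected DLTs seen fall from 18 × 0.20 = 3.6 to 3.6 × 0.95 = 3.42. This ignores how the dose was selected.

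**The case against.** **Surveillance exists.** A reader might infer that nobody looks for toxicity in these 4 weeks. The documents do not support that. They provide for vital signs, examinations and adverse event review at visits, CRS bloods at 1 and 4 hours and on days 1, 2, 5, 10 and 28, lymphocyte numbers by FACS, and a CRS management plan. Symptomatic or CRS-linked toxicity would probably be found. What remains is the isolated laboratory event. The CRS measurements listed are cytokines and CRP, and although that list is worded as open, no routine count or chemistry is named.

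**Other sources may require tests.** The synopsis, the figures, the infusion SOP, the institutional infusion policies and the monitoring plan are not visible. Section 9.1.3 says that TMZ is given as standard of care, so bloods before it restarts are plausible. This stands. It limits the point to the visible schedule, and it rules out the inference that no laboratory test would be done.

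**Nothing contradicts.** Section 9.1.2 defines what counts and Section 13.1 says what is recorded; neither sets a test schedule. That is fair. The fault is a mismatch between endpoint and measurement, not two statements that cannot both be true.

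**The opposite error may be larger.** Patients are infused after TMZ given to reach grade 3 lymphopenia, one grade below the Grade IV rule, and possible attribution is enough. The condition that toxicity be not pre-existing belongs to item e only, so it does not guard against this. As an illustration, take a true rate of 0.10 and an assumed 5% to 20% chance per patient of a falsely attributed count. Then q = 1 − 0.90 × 0.95 = 0.145 to 1 − 0.90 × 0.80 = 0.28, and P(escalate) falls from 0.91 to between 0.82 and 0.54. Those chances have no source in the documents either, but the objection stands as a reason to handle the CBC with care. It does not touch the CMP, which addresses the main gap.

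**Conclusion.** The point holds for the visible text. No CBC or CMP is scheduled between the pre-infusion draw and a date after day 30, for any cycle start from about day 23 to day 31, while hepatic, renal and Grade IV laboratory events inside the window are defined as DLTs. A patient with no laboratory result is still evaluable. Following the plan as written, an unmeasured laboratory DLT counts as none.

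The size is unknown and probably small. The rise of about 1 to 3 points in the chance of passing one dose rests on the assumed 5% unseen share. A reader might infer a badly biased MTD by assuming that a large part of all DLTs, such as half, goes unseen. The documents give no support for such a share, and it would not fit a gap confined to asymptomatic laboratory events. Nor are these figures the chance that the final MTD is too high. The net direction is also not settled, because added counts can produce falsely attributed DLTs.

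It should still be fixed, because it affects how the primary endpoint is ascertained and the remedy is cheap.

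**What to change.** Reconcile Table 6 and Section 12.5 with Sections 9.1.2 and 13.1:

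- Add a CMP, and a CBC with differential, to the draws on days 1, 5, 10 and 28, where immune monitoring and CRS bloods already coincide.
- Have the available results reviewed before each Table 4 decision, and show that a result is missing where a draw was missed.
- Show the pre-infusion count beside each CBC, so that attribution under the existing wording is made against the TMZ-lowered baseline.
- If an SOP or policy already requires these tests, list them in Table 6.

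**Limits.** Days 2–4, 6–9 and 11–27 (3 + 4 + 17 = 24 of 28 days) stay unsampled, so transient events can still be missed. Early samples from the expansion cohort contain ¹¹¹In and need suitable handling. Falsely attributed low counts remain possible and push against escalation.

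**Cost.** No new visit, and no change to the DLT definition, evaluability or replacement. Two more tubes at four draws, at an assumed 3 to 5 mL each, add 24 to 40 mL per patient. The planned volume at those draws is 4 × (9 × 8.5 + 10 + 6) = 370 mL with the Table 6 tubes, or 4 × (50 + 9 + 6) = 260 mL with those in Section 12.8.3 (gold top not counted in either), so the increase is about 6% to 15%. At most (4 × 6 + 12) × 4 × 2 = 288 routine panels are needed before replacements, of which 12 × 4 × 2 = 96 are in the expansion cohort.

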12.1 Screening Examination

A preliminary screening visit will take place prior to the patient undergoing leukapheresis and radiation. In order to not have to repeat clinic visits on back to back days, the standard of care clinic visit can be used to fulfil the initial screening visit requirement. Subject data to be collected at the initial screening examination includes a pathology report, MRI report, CMP and CBC with Differential (just prior to leukapheresis only), and a physical and neurologic examination with KPS score. The patient will then return for the final screening visit after radiation has been completed. Subject data to be collected at the Screening Examination includes CMP and CBC with Differential, a physical and neurologic examination with KPS score, and baseline Curran Status (Curran only performed at post XRT screening). The blood test results from the post radiation screening visit will be the results used to confirm final eligibility. If these test results do not meet the eligibility criteria, the patient can recheck these tests at a local lab up until 6 weeks post radiation in order to be considered eligible for the study. Patients whose lab results do not meet the eligibility criteria by 6 weeks post radiation will be considered a screen failure.

Patients with newly-diagnosed EGFRvIII-positive WHO grade IV malignant glioma will be imaged by MRI for baseline measurements and to assess progression prior to receiving EGFRvIII CARs; although the purpose of this study is not to detect tumor responses, any evidence of tumor response will be determined by serial measures of the product of the 2 largest cross-sectional diameters.^{74,75} For patients with $\geq 25\%$ increase in the product of the largest perpendicular diameters of any enhancing lesion or any new enhancing tumor on MRI scans or unequivocal and significant worsening of non-measurable tumor that is not attributable to co-morbid event or concurrent medication, progression will be defined. Patients may also be classified as progressive disease with significant neurologic decline felt to be due to underlying tumor and not attributable to a co-morbid event or concurrent medication regardless of MRI findings. Note – If there has been a major reduction in steroid dosage in the interval and the patient is felt to be clinically stable or improved, the proper assessment may be “indeterminate” and the therapy could be continued pending the next evaluation. The RANO criteria⁷⁶ will be used for overall assessment of tumor response and pseudoprogression (PRTBTC Imaging SOP and FORM is available upon request). Tumor progression will need to be documented histologically, unless there are clinical contraindications, to exclude inflammatory responses presenting as radiographic or clinical changes, which could indicate potentially toxic or therapeutic responses and not tumor progression. If tissue is obtained, it will be used to confirm tumor progression histologically and to assess immunologic cell infiltration and antigen escape. Upon progression, patients may be treated on other therapies as directed by the treating neuro-oncologist.

12.2 Treatment Period

Patients that have consented onto this study must first undergo a 2 to 4-hour leukapheresis to obtain T cells. After completion of SOC chemoradiotherapy, the treatment period will commence with patients receiving the single infusion of EGFRvIII CARs. The expanded cohort will receive the ¹¹¹In-labeled EGFRvIII CARs.

Infusions will be administered in the BMT Clinic, monitored by an RN during and for 1 hour following the procedure. If a patient develops signs of infection or is febrile prior to the infusion, treatment will be postponed pending clinical work-up. The T cell product will be delivered from the MPACT facility directly to the bedside under the supervision of the research nurse or her designate. For subjects receiving CAR T cells in the expanded cohort, the T cell product that will be labeled with ¹¹¹In will be delivered from the Radiopharmacy. T cells will be administered according to protocol. The patient's name, Study ID, DOB, and MRN will be double verified prior to infusion as is standard Duke BMT transfusion procedure.

The patient will be pre-medicated 30-60 minutes prior to infusion with acetaminophen (650 mg po) and Benadryl (25 mg by mouth) to reduce infusion-related reactions. An intravenous catheter (18-20 G) will be placed for the procedure. The EGFRvIII CARs will be delivered to the patient's bedside in a syringe and applied according to SOP BTC-00069444.01, or the most recent version of the SOP. Vital signs will be assessed prior to and every 15 minutes for 1 hour following the infusion. The infusion

will be documented as well as any adverse experiences with infusion. All Duke transfusion and cell infusion policies will be followed.

Prior to infusion, approximately 65 mLs of blood for IM, RCR PCR assay, and CRS will be drawn (9 yellow top, 1 (10 mL) red top, 1 purple top, and 1 (3mL) red top).

12.3 CRS Management Plan

Grade 1 toxicity

1. Will implement symptomatic management only.

Grade 2 toxicity

1. Monitoring hypotension: we will have clearly established a baseline blood pressure, pre-infusion of CAR T cells, for each patient; if hypotension develops give fluids or 1 low-dose vasopressor.
2. Respiratory symptoms: will be managed by oxygen.

Care for the patients with grade 2 toxicity will be individually tailored, depending on the patient age and medical co-morbidity, and therefore clinical judgement will be crucial prior to use of immunosuppression for Grade 2 toxicity. Patients with Grade 2 toxicity would be monitored in step-down units, including very close cardiac monitoring.

Grade 3 toxicity

1. If grade 3 toxicity develops where fluid resuscitation and low dose vasopressor(s) are not sufficient to reverse the hypotension, or patients require increasing oxygen support or develop grade 3 organ toxicity, the patients will be transferred and monitored closely in intensive care unit. All patients with Grade 3 will receive immunosuppressive agents. In severe cases Tocilizumab, antihuman IL-6R mAb, will be administered. This drug is stocked in the Duke pharmacy.

Grade 4

1. All patients with immediate life threatening toxicity will be treated with full support including mechanical ventilation, immunosuppressive agents, Tocilizumab to prevent inflammatory cascade and with close comprehensive organ monitoring.

